## 3. Data Analysis

There is currently no available data with the use of this device, therefore, we were unable to do a power analysis for sample size determination. This study is therefore considered a pilot project and the results obtained from this study can be used for sample size determination in future clinical trials.

Data will be analyzed quantitatively using VA approved programs, located at Dr. [name]'s office. Following removal of patients' identifiable information except for age and the date of procedure, the data will be transferred to an SPSS worksheet that is installed on a MacBook Pro located at [name] (204C) for further statistical analysis. The output files of the analyses will then reloaded to the Share Point folder and will remain there for future access by the authorized study team members.

## 4. Risks

This project will only offer minimal risk to patients directly related to the use of Pneumoglide device. This device is classified as Class I by FDA which only granted for devices that has minimal risk to patients, and therefore was exempted from obtaining IND number from FDA. The only risk is from possible injuries to lip, teeth and oral mucosa from rough handling of the airway which basically same to patients from either group. Additionally, there may be some difficulty in intubating trachea by novice trainees. All these procedures are performed in the presence and direct supervision by an attending

anesthesiologist with expertise in placing endotracheal tubes. Patient safety is the highest priority and all attending are trained to intervene timely and decrease any potential mishap from occurring.

## 5. Benefits

This study will benefit both future patients of the VA as follow:

- a. Facilitating intubation by improving visualization of the airway (glottis)
- b. Decrease the risk of injury to the teeth, lips and oral mucosa by adding another protective layer
- c. Decrease the risk of gastric aspiration by occluding the esophageal opening while placing the endotracheal tube.

Data Collection tool (Excel Worksheet)

Name	Date	Group	Age	MP	preLG	PostLG	Success	#Att	TTI	FHelp	EsoInt	Inj	GasAsp
Case1													

Variable information:

Name: (Name+Last4)

Date: mm-dd-yy

Group: Device group

Age: years

MP: Mallampathi Classification of the airway

PreLG: Laryngeal grade before insertion of Pneumoglide

PostLG: Laryngeal grade after insertion of Pneumoglide

Success: Successful intubation by the trainee

#Att: Number of the attempts to successfully intubate

TTI: Time to intubate (minutes)

FHelp: Help from the faculty staff

EsoInt: Inadvertent esophageal intubation

Inj: Injury to the lips, teeth and oral mucosa

GasAsp: Gastric Aspiration

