## 1. Introduction/Objective

The proposed study will examine the efficacy of Pneumoglide on facilitating the process of endotracheal intubation while it prevents injury to the upper teeth and aspiration of gastric contents into the lungs. These two complications are among common mishaps during endotracheal intubation by less experienced operators.

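### The only tissue-injury variable covers the three oral sites the device is said to protect and omits the esophageal opening it is said to occlude, so injury there has no column.

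*Combined protocol and SAP*

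**What the plan says.** Section 1 gives the aim as easing intubation while "it prevents injury to the upper teeth and aspiration of gastric contents into the lungs". The worksheet that follows the benefits list in section 5 defines its injury field as "Inj: Injury to the lips, teeth and oral mucosa".

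The same section lists two protective benefits that bear on this field. Benefit (b) is "Decrease the risk of injury to the teeth, lips and oral mucosa by adding another protective layer". Benefit (c) is "Decrease the risk of gastric aspiration by occluding the esophageal opening while placing the endotracheal tube".

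Section 4 recognises injury at the same oral sites and no others: "The only risk is from possible injuries to lip, teeth and oral mucosa from rough handling of the airway". It adds that this risk is essentially the same in both groups.

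Two other worksheet fields relate to safety: "EsoInt: Inadvertent esophageal intubation", and a field for gastric aspiration. Section 2 names trainee success as primary and lists the number of attempts and the time to verified intubation as secondary, with attending assistance also collected. It does not name injury. Section 3 says that no data exist on the device and calls the study a pilot.

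**The concern.** An injury measure in a first comparative study of a device should be able to detect harm where the device acts as well as benefit where it is expected to help. Here the definition matches the list of protected sites exactly and stops there. If staff follow it as written, an abrasion or bleed at the esophageal inlet, or in the pharynx on the way to it, is not an Inj event.

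The stake is how the safety result is read. Injury prevention is part of the aim in section 1, and Inj is the only field that could speak to it. If Inj were compared between groups, a lower rate with the device could be read as less airway injury overall, when it shows only less oral injury.

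**Working it through.** The documents give no injury rate, sample size or injury analysis, so there is no figure to reproduce. The check sets the definitions side by side.

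**Step 1: sites against statements**

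| Site | Said to be protected (section 5, benefit b) | Named as a risk (section 4) | Device said to act there (section 5, benefit c) | Counted by Inj |
|---|---|---|---|---|
| Lips | yes | yes | no | yes |
| Teeth | yes | yes | no | yes |
| Oral mucosa | yes | yes | no | yes |
| Pharynx | no | no | not stated; presumed path | no |
| Larynx | no | no | not stated; adjacent | no |
| Esophageal opening | no | no | yes | no |

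The protected sites and the counted sites coincide, three for three. The one site where benefit (c) places the device is not counted.

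**Step 2: could another column fill the gap?** The 14 columns are Name, Date, Group, Age, MP, preLG, PostLG, Success, #Att, TTI, FHelp, EsoInt, Inj and GasAsp. Apart from Inj, two are safety fields. EsoInt records a misplaced tube and GasAsp records aspiration; neither is tissue damage. There is no column for other injuries or adverse events, no free-text field and no later airway check. The number of columns that record non-oral tissue injury is 0 of 14.

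**Step 3: what an Inj comparison leaves out.** For group g (I or II), let a_g be the proportion of patients with any oral injury, and b_g the proportion with non-oral injury and no oral injury. Then:

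- proportion with any airway injury = a_g + b_g
- proportion that Inj records = a_g
- true difference = (a_I − a_II) + (b_I − b_II)
- difference that Inj shows = a_I − a_II
- part not seen = b_I − b_II

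If Inj favours the device (a_I < a_II), total injury is nevertheless higher with the device whenever b_I − b_II exceeds a_II − a_I. Inj carries no information on b_I or b_II. Neither this condition nor its opposite can be checked from the data as planned.

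**Step 4: are the groups alike at the omitted sites?** Only Group I has a device placed at the esophageal opening. Section 2 also has laryngeal grade documented by direct laryngoscopy before and after device insertion in Group I, and does not collect it in Group II. Exposure at the non-oral sites therefore differs by design, and b_I = b_II cannot be taken for granted.

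**The case against.** The best defence is that Inj fits its hypothesis. Section 1 aims at injury to the upper teeth, section 4 treats the oral sites as the recognised risk, and an oral injury field follows from both. Injury is not a listed primary or secondary outcome, and section 3 specifies no injury analysis, so a between-group injury claim is a plausible use of the data and not a planned one. This limits the weight of the point. It does not supply the missing column.

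Several stronger readings are tempting, and the documents do not support them:

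- **That device-caused harm is scored as no injury.** This is true only at the omitted sites. Device damage to lips, teeth or oral mucosa counts.
- **That Inj can only favour the device.** Benefit (b) is a hypothesis. A device handled by trainees could raise oral injury, and Inj would show it.
- **That the device rests in the larynx or pharynx.** Only occlusion of the esophageal opening is stated. The pharyngeal path is an anatomical inference, and the larynx is merely adjacent.
- **That section 4 contradicts benefit (c).** It is incomplete beside it: its list of risks stops short of the place where the device is said to act.
- **That later trials will inherit a faulty safety estimate.** Section 3 offers the results for sample-size planning and says no more than that.
- **That a numerical bias can be given.** Rates can be assumed that reverse the direction of total injury, or that leave it unchanged. The documents favour neither.

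The consent pages are not in the text reviewed and may describe risks more broadly. That would not alter the worksheet definition.

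**Conclusion.** The point holds as a gap in coverage. The only tissue-injury variable counts every site of claimed protection and omits the stated site of action, and no other column makes this good. Its sensitivity to injury at the omitted sites, when applied as defined, is zero by construction. Whether this matters little or a lot depends on injury rates that the documents do not give, so no size can be attached; the effect could be negligible.

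The conclusion rests on two readings: that a device occluding the esophageal opening touches it, and that staff apply the Inj definition literally. The inclusion of the pharynx rests on anatomy, and that of the larynx on proximity alone. The primary outcome is unaffected. The change should be made, because without it the study cannot support a statement about airway injury beyond the mouth.

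**What to change.** 1. Redefine Inj as any visible airway injury from the lips to the esophageal inlet, with the site coded: lip, tooth, oral mucosa, pharynx, larynx, esophageal inlet. Add a code for blood with no visible source.
2. Record it in both groups by one rule built only on items common to both: visible injury, or blood on the blade, tube or suction. Blood on the device should not count, because Group II has no device and Group I would gain an extra surface on which to score positive.
3. Report oral and non-oral sites separately by group, with blood of unidentified source shown on its own line.
4. State that non-oral differences reflect the whole device procedure, including the laryngeal grading before and after insertion in Group I, and not the device alone. The additional viewing may also give more chance to see an injury in Group I.
5. Reconcile the section 4 statement on risk with benefit (c).

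A sore-throat question in the recovery room is optional. It would add an assessment time point in both groups and is not needed to close the gap.

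The cost is a wider definition, a site code and a wording change in section 4. The downside is that the injury rate reported for the device may look less favourable.
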